**Secondary Outcomes:**

1. Using the BISQ, we will compare the following metrics between the control vs BID and control vs TID groups at every 3 month interval for the total study duration ( up to 18 months on therapy).
  - a. Total awake time per night
  - b. Qualitative assessment of difficulty falling asleep
  - c. Time to fall asleep
  - d. Longest sleep stretch per night
2. Clinical Response to Medication
  - a. Qualitative clinical assessment on size, color changes of hemangiomas
3. Evaluation of potential side effects

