**Sample Size:**

A sample size calculation was performed using best estimates in the literature provided by Theiler et al. (Theiler et al., 2021). Primary outcome was defined as number of awakenings per

night of sleep at 6 months of time on propranolol. In the Theiler et al study, patients on propranolol had 0.26 +/- 0.09 vs control patients of 0.21 +/- 0.1 awakenings per night. Utilizing a two-tailed analysis, we anticipate enrollment of 58 patients per treatment arm, giving our study 80% power with alpha 0.05. Given our number of annual patients (approximately 60 per year), we anticipate this study to be performed in 3 years. A concurrent Bayesian analysis will be performed.

We will analyze the data as two separate studies, each using the control (timolol) group as the reference. The BID propranolol group will be compared to the control group, as well as the TID group compared to control. This will allow us to see the effective change of sleep awakenings in each dosage group compared to control.

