### Blinding:

This is an open label study so patients and providers will not be blinded.

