### Prescription:

1. Control group: Patients with a small (<2cm) isolated infantile hemangioma are prescribed timolol 0.5% ophthalmic drops, a topical beta-blocker. Topical timolol has not demonstrated any concerns for sleep disturbances. Therefore, these patients will be enrolled as control patients in a non-randomized fashion.

Dosage for timolol 0.5% is 1 drop BID directly onto the hemangioma

2. Study groups: Patients with larger (>2cm) or multiple (>1) hemangiomas will be randomized to BID or TID dosage of propranolol. The prescription will be sent electronically to the pharmacy in the standard fashion for the practice. All patients will be initiated with the following schedule with medication administration to follow feeding:

Week 1: 0.5 mg/kg/day divided BID or TID

Week 2: 1 mg/kg/day divided BID or TID

Week 3: 2 mg/kg/day divided BID or TID. Patients will stay on this dosage until their 3 month follow up visit.

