### Sleep Survey:

In this study, we propose to use the Brief Infant Sleep Questionnaire (BISQ) to record and quantify caregiver reports of infant sleep. The BISQ has been validated as a multi-dimensional survey for evaluating infant sleep due to its reliability and high specificity of sleep parameters (Sadeh, 2004; Del-Ponte et al., 2020). Parents will be offered this study at each of the clinic visits (every 3 months) from the date of initial prescription until termination of the medication (18 months of age). Patients in all three groups (Timolol, BID Propranolol, and TID Propranolol) will be given this survey.

Follow up: Once a prescription is initiated, all patients with infantile hemangiomas stay on the medication until 18 months of age. Patients are seen every three months, either in person or virtual visits. During that visit, a recent weight is used to adjust their dosage of the oral propranolol to the new appropriate level. Each of these visits will be an opportunity for the sleep survey to be given.

Study Termination: After 18 months of age, all patients are removed from medication (timolol and propranolol). After this visit and final sleep assessment, all patients will be removed from the study.

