### Data Collection

1. Patient demographic information: name, date of birth, birth history, race, ethnicity, gender.
2. Location(s), measurements, and photos of vascular malformation(s)
3. BISQ sleep survey
  - a. Timing: Every 3 months\

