### **Confidentiality**

Research data will include any personal health information that can be used to identify the patients. All medical records are imported directly into the EPIC system, including prescriptions and patient photos. BSIQ Sleep records will always be kept on a password locked computer in the Principal Investigator's locked office and information will be transcribed into a Redcap database that has been created for this study using the UTHHealth platform. Release of information will only occur with de-identified data for research purposes. Patient information will only be accessible via the University of Texas Health Science Center at Houston's encrypted file sharing program. This program will not allow the data to be downloaded, only viewed.

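### The only efficacy outcome is an undefined qualitative judgement in an open-label study, while the lesion measurements listed for collection enter no outcome or analysis

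*Combined protocol and SAP*

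**What the plan says.** Secondary Outcomes, item 2, is the only place where the plan defines a treatment response of the lesion. The whole definition is "Qualitative clinical assessment on size, color changes of hemangiomas". The plan does not say how many grades the judgement has, who makes it, when, or which groups are compared.

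The Blinding section states: "This is an open label study so patients and providers will not be blinded". No independent or masked reader is mentioned anywhere.

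Data Collection includes "Location(s), measurements, and photos of vascular malformation(s". Only the sleep questionnaire in that list has a timing, every 3 months. Photos are kept in the clinical record (Confidentiality: "All medical records are imported directly into the EPIC system, including prescriptions and patient photos"). On follow-up, the Sleep Survey section says: "Patients are seen every three months, either in person or virtual visits".

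On comparisons, the Prescription section says "Patients with larger (>2cm) or multiple (>1) hemangiomas will be randomized to BID or TID dosage of propranolol", while infants with a small single lesion receive timolol without randomisation. The Sample Size section says: "We will analyze the data as two separate studies, each using the control (timolol) group as the reference".

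**The concern.** The plan lists a quantitative size measure for collection but defines its size outcome as an impression. Two consequences follow.

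- **Bias.** Providers know the regimen. A judgement with no scale, time point or named assessor gives expectation more room than a recorded dimension does. The plan does not name the assessor. That it is an unblinded provider is an inference from the open-label design and the word clinical, and nothing contradicts it.
- **Precision.** A rating with few grades carries less information than a measurement of the same change, and 58 infants per arm is a small base.

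The research question and PICO ask whether TID dosing improves sleep relative to BID. A sleep gain would be of practical use only if lesion response were not worse, and this outcome is all the plan offers on that point. The randomised TID and BID arms are where it can be answered fairly. Timolol patients are selected for a single lesion under 2 cm and receive a different drug, so lesion response against them is confounded by starting size.

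**Working it through.** **1. The plan's own figure.** The only stated calculation concerns awakenings, not lesions. Inputs from Sample Size: "patients on propranolol had 0.26 +/- 0.09 vs control patients of 0.21 +/- 0.1 awakenings per night", two-sided alpha 0.05, power 80%.

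- Pooled SD = √((0.09² + 0.10²)/2) = √0.00905 = 0.0951; difference = 0.26 − 0.21 = 0.05.
- n per arm = 2 × (1.960 + 0.842)² × 0.00905 / 0.05² = 56.8, so 57. The t-test version gives 57.8, so 58.
- Power at 58 per arm is 0.808 (normal) or 0.801 (t-test).

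The stated 58 per arm reproduces. The plan gives no power, precision target, effect size or SD for clinical response. Everything below is therefore illustration, assuming 58 TID and 58 BID infants, no dropout and a normally distributed size change.

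**2. Analysed as a measurement.** The difference detectable with 80% power is (1.960 + 0.842) × √(2/58) = 0.52 SD. The 95% confidence interval half-width is 1.960 × √(2/58) = 0.36 SD.

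**3. The same 0.52 SD difference analysed as a rating.**

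| Rating | Power at 58 per arm | n per arm for 80% |
|---|---|---|
| 2 categories, 50% vs 30% respond | 59% | 95 |
| 2 categories, 60% vs 39% | 60% | 92 |
| 2 categories, 70% vs 50% | 59% | 95 |
| 2 categories, 80% vs 63% | 55% | 105 |
| 3 categories (simulation, Mann-Whitney) | 70% | – |
| 5 categories (simulation, Mann-Whitney) | 74% | – |

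The second proportion in each two-category row is the first moved down by 0.52 on the normal scale.

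**4. The information figure.** A split at the median of a normal variable has relative efficiency 2/π = 0.637. With 2 × 58 = 116 randomised infants, 116 × 0.637 = 74. This agrees with the table (58/92 = 0.63). A cut well away from the median loses somewhat more (58/105 = 0.55), and three or five grades lose far less.

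**5. Measurement error.** A measurement is not error-free either. If its reliability were 0.9 or 0.8, its 80% power would fall to 76% or 71%. A rating has error of its own, and the documents give no figure for either.

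**The case against.** The strongest objection is that serial measurements may not exist. Data Collection gives lesion measurements no timing and lists them beside one-time items such as date of birth. Treatment allocation depends on a 2 cm cut, so a baseline measurement alone would fit the text. The follow-up description mentions weight-based dose adjustment and the survey, not the lesion, and visits may be virtual. This stands. A reader might infer that follow-up measurements are already in hand and that using them costs nothing, but the documents do not show it. What remains is that a ruler measurement at an in-person visit that takes place anyway needs no extra staff.

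Second, the same unblinded staff would presumably hold the ruler. This also stands. Measurement narrows the room for expectation without removing it.

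Third, a reader might infer that the plan contains a TID versus BID efficacy check that is carried out badly. It does not. Clinical response has no named comparison, and the analysis statement covers only comparisons with timolol. The TID versus BID response contrast has to be added.

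Fourth, the plan does not bar clinicians from consulting measurements when they judge size, so it is not shown that information is discarded. That is fair, but nothing requires them to do so or says how.

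Finally, this is a secondary outcome in a sleep trial, and both propranolol arms share the same total daily dose schedule. That limits the consequence but does not supply a definition for the only efficacy outcome.

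**Conclusion.** The point holds as a minor improvement. The only efficacy outcome is an undefined qualitative judgement made in an open-label study, and the measurements listed for collection feed no outcome or analysis. A defined measurement is a better size outcome because it reduces, without eliminating, the scope for expectation bias and should improve precision.

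The size of the gain cannot be derived from the documents. The 64% figure, with 116 infants informing like 74, belongs to the coarsest scale, two categories split at the median, under normality, no dropout and error-free measurement. It should not be read as the expected loss, because the plan states no number of categories. With three to five grades, power under the same assumptions would be 70% to 74% instead of 80%. The primary sleep comparisons are not affected.

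**What to change.** Add to Secondary Outcomes, item 2:

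- Size response is the recorded measurement of one target lesion, fixed at first prescription (for example the largest), taken at baseline and at in-person follow-up visits including 6 months.
- It is compared between the randomised TID and BID arms by a regression of log follow-up size on arm, adjusted for log baseline size and age, and reported with a 95% confidence interval. State in advance how a lesion that is no longer measurable is handled, since its log size is undefined.
- The qualitative judgement is kept for color and as a supporting overall assessment.

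Add a timing for lesion measurements to Data Collection, matched to the sleep survey visits held in person.

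The cost is a few sentences, a short measurement at existing visits and one simple model. There are three downsides: follow-up measurement becomes a scheduled procedure, values will be missing at virtual visits, and a single target lesion does not describe infants with several lesions.

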**Sample Size:**

A sample size calculation was performed using best estimates in the literature provided by Theiler et al. (Theiler et al., 2021). Primary outcome was defined as number of awakenings per

night of sleep at 6 months of time on propranolol. In the Theiler et al study, patients on propranolol had 0.26 +/- 0.09 vs control patients of 0.21 +/- 0.1 awakenings per night. Utilizing a two-tailed analysis, we anticipate enrollment of 58 patients per treatment arm, giving our study 80% power with alpha 0.05. Given our number of annual patients (approximately 60 per year), we anticipate this study to be performed in 3 years. A concurrent Bayesian analysis will be performed.

We will analyze the data as two separate studies, each using the control (timolol) group as the reference. The BID propranolol group will be compared to the control group, as well as the TID group compared to control. This will allow us to see the effective change of sleep awakenings in each dosage group compared to control.

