**Primary Outcome:**

1. Using the BISQ, number of sleep awakenings per night between the control (timolol) group and the BID propranolol group at 6 months on therapy.
2. . Using the BISQ, number of sleep awakenings per night between the control (timolol)group and the TID propranolol group at 6 months on therapy.

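### The 80% power at 58 per arm holds only if the between-infant SD of the BISQ awakenings answer is about 0.095 or less, and the plan does not show that it is

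*Combined protocol and SAP*

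**What the plan says.** The Sample Size section introduces its planning values with "A sample size calculation was performed using best estimates in the literature". It takes them from a single cohort study: "patients on propranolol had 0.26 +/- 0.09 vs control patients of 0.21 +/- 0.1 awakenings per night". From these, with a two-tailed test, it concludes: "we anticipate enrollment of 58 patients per treatment arm, giving our study 80% power with alpha 0.05". Three arms of 58 make the total of 174 on the front page. The section does not say whether ± is an SD, a standard error or an interval half-width, and it does not name the instrument behind the values.

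The Primary Outcome section takes the endpoint from the BISQ, at 6 months on therapy: "Using the BISQ, number of sleep awakenings per night between the control (timolol) group". The Sleep Survey section uses the questionnaire "to record and quantify caregiver reports of infant sleep" and ties it to the three-monthly clinic visits: "Each of these visits will be an opportunity for the sleep survey to be given". The Data Collection section gives the same schedule ("Timing: Every 3 months"). No section describes averaging over recorded nights, states whether the awakenings item is answered in whole numbers, gives an SD for it, or shows how power changes with the SD.

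**The concern.** The sample size depends on the ratio of 0.05 to the SD. An SD near 0.095 is small for a quantity whose mean is about a quarter of an awakening per night. It could arise if each infant's value were an average or a fractional answer. It cannot arise from single whole-number answers at those means. The plan's description of its endpoint, a number reported once per visit, does not show which of these applies.

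Both primary comparisons, BID against timolol and TID against timolol, use this one SD. If the BISQ SD is materially larger, a null result in either comparison would say little about a difference near 0.05, yet it could be read as showing no sleep effect.

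**Working it through.** **Inputs.** From the Sample Size section: means 0.26 and 0.21 (difference 0.05), ± 0.09 and ± 0.10, 58 per arm, two-sided alpha 0.05. From the Primary Outcome and Sleep Survey sections: BISQ awakenings per night, one survey per visit. Not given: the response format of the item and the meaning of ±.

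**1. The plan's own figure.** Reading ± as an SD:
- Pooled SD = √((0.09² + 0.10²)/2) = √0.00905 = 0.0951.
- Standardised difference = 0.05/0.0951 = 0.526.
- Noncentrality = 0.05/(0.0951 × √(2/58)) = 2.83, with 114 degrees of freedom and critical t 1.981.
- Power is 80.1%, and n for 80% is 57.8, so 58 per arm. The figure reproduces.

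**2. The SD ceiling.** Solving the same t-test for the largest common SD that gives 80% power for 0.05 at 58 per arm yields 0.0953 (0.0961 by the normal approximation). The plan's value sits almost exactly at that limit.

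**3. Sensitivity at 58 per arm** (t-test, common SD):

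| SD | Power for 0.05 | Difference detectable with 80% power |
|---|---|---|
| 0.095 (plan) | 80% | 0.050 |
| 0.10 | 76% | 0.052 |
| 0.15 | 43% | 0.079 |
| 0.20 | 27% | 0.105 |
| 0.30 | 14% | 0.157 |
| 0.42 (whole-number minimum) | 10% | 0.222 |
| 0.485 (Poisson) | 8.5% | 0.254 |

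Power is 50% at an SD of 0.136.

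**4. Where the last two rows come from (assumption: whole-number answers, means 0.21 and 0.26).** For a count X of 0, 1, 2 and so on, X² is never less than X. The variance is therefore at least m − m² = m(1 − m), where m is the mean.
- Control: √(0.21 × 0.79) = 0.407. Propranolol: √(0.26 × 0.74) = 0.439. Pooled: √((0.1659 + 0.1924)/2) = 0.423.
- Power for 0.05 is 9.7% by noncentral t and 10.0% by exact enumeration of 0/1 answers. This uses the smallest possible variance, so it is an upper figure for whole-number answers.
- Poisson variance: pooled SD √((0.21 + 0.26)/2) = 0.485, power 8.5%.
- 80% power for 0.05 would need about 1,126 (0/1) or 1,477 (Poisson) per arm.

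**5. Larger effects under the same assumption.** Holding the control mean at 0.21 and letting the SD follow the mean in the propranolol arm, the difference detectable with 80% power is about 0.24 (0/1) to 0.32 (Poisson), roughly five to six times the planned 0.05. These exceed the last two table rows because the variance grows with the mean.

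**The case against.** The best defence is that the plan contains no arithmetical error. It names its source, which the reference list shows to be a cohort study of sleep in infants with hemangioma treated with propranolol, so the population is close. If that source reports between-infant SDs on a comparable measure, the 80% stands. Nor does power collapse just above the ceiling: it is 68% at an SD of 0.11 and 60% at 0.12, and it rises to 92% at 0.08. All of this stands.

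The defence can also say that the 10% scenario keeps the cited means while discarding the cited spreads. That is fair, and it cuts both ways. If 0.09 and 0.10 are between-infant SDs, the source values cannot be single whole-number answers, and the plan must show that its BISQ answers are on the same footing. If they are not between-infant SDs, the 80% has no basis.

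A reader might infer that the trial simply has 10% power, that ± must be a standard error, or that the calculation is wrong. The documents support none of these. They do not give the response format, what ± denotes or the source instrument. Fractional typical-night answers could have a smaller SD, and BISQ means other than 0.21 and 0.26 would change both the minimum SD and the relevant difference.

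The concurrent Bayesian analysis mentioned in the Sample Size section does not resolve the point. It is not specified, and it does not supply the missing SD.

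**Conclusion.** The point holds as a conditional one. The calculation is correct for the inputs used, but the 80% is stated without the condition on which it depends: a between-infant SD of about 0.095 or less for the BISQ awakenings answer at 6 months. Nothing in the plan establishes that condition, and there is almost no slack (ceiling 0.0953 against 0.0951 used).

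The size of the shortfall cannot be fixed from the documents. It runs from none, if the SD is confirmed, through 43% power at 0.15 and 27% at 0.20, to at most about 10% if answers are whole numbers at the planned means. Confidence in the dependence on the SD is high. Confidence in any particular power figure is limited by the missing response format and the unlabelled ±.

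**What to change.** In the Sample Size section, in this order:

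1. Check the cited study. State what ± represents, which instrument produced the values, and how the BISQ item is scored in this trial (whole or fractional, and over what recall period).
2. Unless this confirms a between-infant SD of about 0.095 on the scale used here, replace the single 80% with the power for 0.05 and the detectable difference at 58 per arm over a range of SDs that includes the plan's value, as in the table above. Restate 0.05 if the BISQ means differ from 0.21 and 0.26.
3. Update that statement with an SD pooled over all arms, computed without group labels, from BISQ responses at visits already scheduled, with no change to enrolment. Treat it as provisional until 6-month responses exist, because earlier visits may have a different SD. Ignoring labels inflates the SD slightly: with one arm at 0.21 and two at 0.26, it adds (2/9) × 0.05² = 0.00056 to the variance, so a true 0.095 would appear as about 0.098.

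The cost is one rewritten paragraph, one look at the source and one SD calculation, with no extra patients, visits or forms. A larger trial is not proposed: about 60 patients a year for three years is 180, which leaves little room above 174. The downside is a less favourable stated power.

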**Research Question:**

In patients with infantile hemangioma, does three times a day (TID) dosing versus twice a day (BID) dosing of propranolol significantly improve subjective sleep scores?

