Overall, oral beta blockers have been the mainstay treatment for hemangiomas, but their association with sleep disturbances has continued to frustrate parents. Propranolol exhibits strong penetration into the blood brain barrier due to its lipophilicity. This penetration is likely exaggerated by the increased permeability of the blood brain barrier in infants (Vivas-Colmenares et al., 2015). Pediatric patients are thus at even higher risk of CNS side effects such as sleep disturbance and agitation. Parent reports of sleep impairments includes nightmares, insomnia, restlessness, increased waking, and overall sleep disturbance (Xerfan et al., 2020). While these sleep disturbances may be considered a minor side effect, the issue is cited as the most common reason for early discontinuation of propranolol (Ji et al., 2018).

The standard dosing regimen for oral propranolol for the treatment of infantile hemangiomas is twice a day (BID) dosage. In our multidisciplinary vascular anomalies clinic, parents of infants on propranolol for hemangiomas are queried at each visit regarding side effects. If a parent discusses concerns regarding sleep patterns, our standard protocol is to alter the regimen to three times a day (TID) dosage. While this seems to improve the sleep symptoms, there is no evidence to support this dosing schedule. The purpose of this study is therefore two-fold:

1. Assess the baseline sleep pattern disruption for patients starting oral propranolol at the standard BID dosing regimen compared to the control (timolol) group.
2. Determine if there is a significant improvement in the sleep patterns in infants taking oral propranolol on the TID dosing regimen versus the control (timolol) group.

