## PICO

P: In patients with infantile hemangiomas  
I: does TID dosing of oral propranolol versus  
C: standard BID dosing of oral propranolol  
O: result in a significant improvement in subjective sleep scores

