**Hypothesis:**

We anticipate that patients receiving the TID dosing regimen of oral propranolol will demonstrate fewer sleep awakenings compared to the control group than the BID dosing regimen compared to the control.

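### The stated question, and the only randomised contrast, is TID versus BID, but the plan tests and powers only comparisons of each regimen with non-randomised timolol controls

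*Combined protocol and SAP*

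**What the plan says.** The sections fall into two groups.

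**TID versus BID.**
- The Research Question asks "does three times a day (TID) dosing versus twice a day (BID) dosing of propranolol significantly improve subjective sleep scores".
- PICO names the comparator as "standard BID dosing of oral propranolol".
- The Hypothesis is that TID patients "will demonstrate fewer sleep awakenings compared to the control group than the BID dosing regimen compared to the control".
- Under Prescription, children with larger or multiple hemangiomas are randomised to BID or TID. Children with a small isolated lesion receive timolol and enter as controls without randomisation.

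**Each regimen versus timolol.**
- The two purposes at the end of Background and Significance are both framed against the timolol group.
- Primary Outcome lists awakenings per night at 6 months for control versus BID and for control versus TID. The sleep items under Secondary Outcomes use the same two pairs.
- Sample Size says: "We will analyze the data as two separate studies, each using the control (timolol) group as the reference".

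The planning figures come from a cited cohort in which "patients on propranolol had 0.26 +/- 0.09 vs control patients of 0.21 +/- 0.1 awakenings per night". The power statement follows: "Utilizing a two-tailed analysis, we anticipate enrollment of 58 patients per treatment arm, giving our study 80% power with alpha 0.05". The section also says "A concurrent Bayesian analysis will be performed", with no model, prior or contrast. No section gives a test, effect size or power for TID against BID.

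**The concern.** The Hypothesis is worded through the control group, but it is a statement about TID minus BID: (TID − control) − (BID − control) = TID − BID. The control mean cancels. Research Question, PICO and Hypothesis therefore all ask for one contrast. Randomisation protects that contrast, and the plan does not analyse it.

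Two things follow. First, if the plan is carried out as written, the main question is left to an informal reading of two separate p-values against a shared, non-randomised control. One significant and one non-significant result is not a test of the difference between them, and it can suggest a TID benefit where there is none. Second, the 80% is the only power figure in the document, so it may be quoted for the main question although it was calculated for a different one.

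**Working it through.** **Inputs (Sample Size section).** Means 0.26 and 0.21, so a difference of 0.05; ± values 0.09 (propranolol) and 0.10 (control), read as SDs; 58 per arm; two-sided alpha 0.05; no adjustment for two comparisons and no allowance for losses. Assumed, because the documents do not give them: the BID SD is 0.09, as in the cited propranolol group, and the TID SD lies between 0.09 and 0.10.

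**1. Reproduce the plan's figure.**
- Pooled SD = √((0.09² + 0.10²)/2) = 0.0951.
- Two-sample t-test (noncentral t), difference 0.05: 57 per arm gives 79.4% power and 58 per arm gives 80.1%.

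The 58 is therefore the t-test answer for one propranolol arm against control, and 3 × 58 = 174 matches the stated total. The arithmetic is right for either control comparison, if that comparison has a true difference of 0.05.

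**2. What 58 per arm gives for TID versus BID.**
- SE = √((SD_TID² + SD_BID²)/58).
- SDs 0.09/0.09: SE = 0.0167. The difference detectable with 80% power is 0.0472, and the 95% CI half-width is 1.981 × 0.0167 = 0.033.
- SDs 0.10/0.09: SE = 0.0177. The detectable difference is 0.0499, and the half-width is 1.981 × 0.0177 = 0.035.

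If the 0.05 is taken as the BID excess over control, TID would have to remove nearly all of it (0.047/0.05 = 94% or more) for the direct comparison to have 80% power.

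**3. Can the two control tests replace the direct one?** Suppose BID and TID have the same true excess of 0.05, so that there is no TID benefit.
- SE of each control comparison = √((0.09² + 0.10²)/58) = 0.01767.
- Expected test statistic = 0.05/0.01767 = 2.83, against a critical value of 1.981.
- Correlation of the two statistics through the shared control = 0.10²/(0.10² + 0.09²) = 0.55.

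From the bivariate normal with these values, and from simulation with t-tests (all SDs as above, TID SD 0.09):

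| Result against control | Share of trials |
|---|---|
| Both significant | about 69% |
| BID significant, TID not | about 11% |
| TID significant, BID not | about 11% |

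The two tests would disagree in about one trial in five although the regimens are identical. In half of those the pattern would look like a benefit of TID.

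**4. Illustration only.** If 0.05 is the BID excess and TID halves it (true difference 0.025), power is 29% for TID versus control (SDs 0.09/0.10) and 29% to 32% for TID versus BID. If the BID excess is 0.10 and TID halves it, both differences are 0.05, and power is 80% and 80% to 84%. The documents give neither the share removed nor the regimen to which the 0.05 applies, so these figures show only how far the power depends on unstated assumptions.

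**The case against.** The strongest reply is that the plan is consistent within itself. The sentence before the power claim gives propranolol against control, the next paragraph names the two control comparisons, and the stated purposes in Background and Significance are both against timolol. Read in context, the 80% belongs to propranolol versus control. This stands: for that contrast the gap is one of labelling. It does not remove the conflict with Research Question, PICO, Hypothesis and the randomisation.

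A reader might also infer some stronger criticisms that the documents do not support.

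- *That one 0.05 cannot serve both control comparisons, because the Hypothesis makes the TID excess smaller.* A planning difference is the value at which power is evaluated, not a claim that both true effects equal it. Using one value for two comparisons is ordinary practice.
- *That the plan will treat a non-significant TID result as proof that TID sleep matches control.* No section says so. The plan promises only the change in each dosage group relative to control.
- *That the trial has about 29% power for its main question.* That rests on an assumed share of the excess removed by TID.

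The Bayesian analysis could in principle address TID versus BID, but nothing in its single sentence says that it will.

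**Conclusion.** The point holds as a mismatch between question and analysis. Research Question, PICO and Hypothesis ask about TID versus BID, and only that contrast is randomised. Every planned sleep comparison is against non-randomised timolol controls, and the only stated power applies to those. As written, the plan leaves its one randomised contrast untested.

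The size, from the plan's own figures: 80.1% power for each control comparison at 0.05; for TID versus BID, 80% power only at about 0.047 to 0.050; and about an 11% chance of a misleading pattern favouring TID if both regimens share a 0.05 excess. These figures assume that the ± values are SDs of awakenings per child, that the TID SD is 0.09 to 0.10, and that all 58 per arm are evaluable at 6 months.

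It would be tempting to conclude that 58 per arm is wrong or that more patients are needed. The documents do not support that: 58 is correct for the comparisons it was calculated for, and no target difference for TID versus BID is given against which it could be judged too small.

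**What to change.** Keep 58 per arm, and make these changes.

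1. In Primary Outcome and Sample Size, add the direct TID minus BID comparison of awakenings per night at 6 months between the randomised arms, with its estimate and 95% CI, as the analysis that answers the Research Question.
2. State its place relative to the two control comparisons in the use of alpha. The plan at present gives 0.05 with no allocation between comparisons.
3. Replace the power sentence with wording such as: *58 per arm gives 80% power for each propranolol-versus-control comparison at a true difference of 0.05 awakenings per night (SDs 0.09 and 0.10, two-sided alpha 0.05, no losses); for TID versus BID, 58 per arm gives 80% power only for a difference of about 0.047 to 0.050 (assuming a TID SD of 0.09 to 0.10).*
4. State that a benefit of TID over BID will not be inferred from one control comparison being significant and the other not.

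The illustrative power figures for assumed shares need not go into the protocol.

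The cost is a few reworded sentences. The direct comparison uses data already being collected and needs no extra patients. The downsides are a less favourable power statement for the main question and one further comparison to place in the use of alpha.
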